Upon consent, patients will be electronically randomized to one of the two treatment arms. Patients in the control arm will proceed directly to surgery. Patients in the intervention arm will have an MRI performed after randomization and before treatment. If the interval from CT to MRI is >14 days, a new CT will be performed to assure a valid comparator. The MRI will be read by an experienced gastro-radiologists blinded to the patient's identity and initial CT scan. Based on the MRI, the treatment decision will be made (*Figure 2*):

Figure 1. Study design. R: Randomization.

- 1) No liver metastases on MRI (expected ~75%): Surgery as planned.
- 2) Non-specific liver lesions on MRI, not seen on CT (expected $\sim 10\%$): Surgery as planned.
- 3) Liver metastases on MRI (expected ~15%): Referral to liver biopsy and oncological treatment if malignancy is verified. If biopsy is inconclusive, repeat liver MRI after one month.

[figure not shown]

Figure 2. Patient flow in the intervention arm. MDT: Multidisciplinary team conference.

Follow-up

Patients will be followed for up to three years for information on treatment, recurrence, and vital status. We will conduct standard-of-care follow-up CT at 3, 6, 9, 12, 18, 24, 30, and 36 months postoperatively in all patients. Primary end-point for this project will be one-year survival. For subsequent studies, we will also perform analyses of three-year survival.

SPECIFIC STUDY AIMS, HYPOTHESES AND OUTCOMES

Study I: To compare tumor staging of pancreatic cancer patients assessed by MRI versus upper abdominal CT.

Study II: To assess the ability of MRI to detect liver metastases in pancreatic cancer patients with resectable tumor on CT.

Study III: To assess the impact of MRI on treatment allocation, recurrence, and survival in pancreatic cancer patients with a resectable tumor on CT.

Details of study hypotheses, population, and analytical plans are outlined in Figure 3.

	Study I	Study II	Study III
Aim	To compare tumor	To assess the ability of	To assess the impact of
	staging of pancreatic	MRI to detect liver	MRI on treatment
	cancer patients assessed	metastases in pancreatic	allocation, recurrence,
	by MRI versus upper	cancer patients with	and survival in pancreatic
	abdominal CT	resectable tumor on CT	cancer patients with a
			resectable tumor on CT
Hypothesis	MRI is non-inferior to CT	MRI will detect liver	Use of MRI will change
	with respect to tumor	metastases in patients	treatment allocation and

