	staging	with a resectable tumor	improve overall survival
		on CT	
Population	Patients in the	Patients in the	Patients in both arms
	intervention arm (N=100)	intervention arm (N=100)	(N=200)
Analysis	Agreement assessed by	Agreement assessed by	Treatment allocation and
	intraclass correlation	intraclass correlation	recurrence by Chi ² test
	coefficient (ICC)	coefficient (ICC)	Survival analyses by
			Kaplan-Meier estimation

Figure 3. Outline of the three studies.

POWER CALCULATIONS AND FEASIBILITY

Assuming alpha=0.05, power of 80%, and a hazard ratio of death of 1.5, we need 191 patients in total. To guard against dropout of 5%, we aim to include 200 patients. On average, all four institutions performing pancreatic cancer surgery in Denmark (Rigshospitalet, Aarhus, Aalborg, and Odense) shall include 50 patients. We aim to finalize patient enrollment during the first 18 months of the study period, equaling to 2.8 patients monthly in each institution. In total, ~300 resections will be performed during this 18-month period. We consider it feasible and realistic to include two-thirds of these patients.

IMAGING PROTOCOLS

CT imaging protocol

As a part of the routinely workup for staging pancreatic cancer, all patients referred to the local hepato-pancreato-biliary MDT board undergo a pancreas-specific CT scan. All CT scans include a

portal venous phase (PVP) of the liver. CT scanners from different vendors will be used to acquire the images. The PVP will routinely obtained by 120 KV and mAs range from 150 to 290 depending of the body mass of the patient and the scan system. Contrast medium will be administered intravenously as a bolus injection by weight bases contrast Iodine concentration of 500 – 750 mg I/kg and a rate of 3-5 ml/s, followed by a saline flush of 20–40 ml. The scan delay for the PVP will be 50 sec (post-threshold, bolus tracking). Axial slice thickness of 2 mm slices will be reconstructed with 1 mm increments.

MR imaging protocol

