Beside the salary for [name] and two research nurses mentioned above, we apply the Danish Cancer Society for expenses related to MRI scans. The departments will hold expenses for CT scans for the 50% of the patients that are expected to have more than 14 days between CT and MRI. Please see the attached budget for more details.

FUTURE PERSPECTIVES

We expect this project to substantially improve our ability to tailor the optimal treatment for each individual with pancreatic cancer. Underdiagnosis of liver metastases delays the initiation of life-prolonging chemotherapy. Thus, with proper preoperative detection of liver metastases, our project will improve both survival and quality-of-life, as patients will be spared from unnecessary major surgery. Thus, findings from our project is expected to have an immediate clinical impact. Furthermore, if MRI is non-inferior to CT with respect to tumor staging, it may replace CT in the diagnostic workup of pancreatic cancer patients.

ETHICAL CONSIDERATIONS

This project will be conducted according to the Helsinki Declaration. The project needs to be registered at the Danish Data Protection Agency in accordance with the Central Denmark Region common registration system and it also requires approval from the Central Denmark Region Ethics Committee. We will ensure that all permissions are granted when study starts. All information involving patients will be handled according to national law on personal data information. Both positive, negative, and inconclusive results will be published, and presented at scientific meetings. Results will be presented at international scientific congresses, and we will aim for publications in

high-impact journals with focus on oncology, radiology, and surgery. The study will be registered at ClinicalTrials.gov and monitored by the Good Clinical Practice Unit at Aarhus University Hospital.

REFERENCES

- Gillen S, Schuster T, Meyer Zum Buschenfelde C, Friess H, Kleeff J.
 Preoperative/neoadjuvant therapy in pancreatic cancer: a systematic review and metaanalysis of response and resection percentages. PLoS Med. 2010;7: e1000267.

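### The 80% power depends on a whole-arm hazard ratio of 1.5 that is not derived from the roughly 15% of MRI patients whose treatment can change, and on 191 deaths counted as patients

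*Combined protocol and SAP*

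**What the plan says.** The sample size paragraph (POWER CALCULATIONS AND FEASIBILITY) reads: "Assuming alpha=0.05, power of 80%, and a hazard ratio of death of 1.5, we need 191 patients in total". The total is then raised to 200 for 5% dropout. No source or derivation is given for the 1.5, and no control survival rate or expected number of deaths is stated.

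The Follow-up section fixes the endpoint: "Primary end-point for this project will be one-year survival". Study III compares survival between both arms, N=200, by Kaplan-Meier estimation.

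The section Study design and patient flow says who is treated differently:

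- Controls: "Patients in the control arm will proceed directly to surgery".
- MRI arm, first group: "No liver metastases on MRI (expected ~75%): Surgery as planned".
- MRI arm, second group: "Non-specific liver lesions on MRI, not seen on CT", expected in about 10%, who also go on to the planned operation.
- MRI arm, third group: "Liver metastases on MRI (expected ~15%): Referral to liver biopsy and oncological treatment if malignancy is verified".

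The background cites two yields of MRI-only liver metastases in patients judged resectable or non-metastatic on CT: 5% in a retrospective study of 216 patients and almost 25% in a prospective study of 69.

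**The concern.** On the protocol's own figures, 75% + 10% = 85% of the MRI arm is managed as the controls are. In the written flow a survival difference between the arms can therefore come only from the remaining 15% or so, and only from those in whom malignancy is verified. An HR of 1.5 averaged over all 100 MRI patients asks a great deal of about 15 of them. Nothing in the power paragraph links the two figures.

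The paragraph also treats a count of deaths as a count of patients, which lowers the power whatever the true effect is.

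At stake is what the survival comparison can show. The stated aim is to increase overall survival, and the 80% is the only figure that tells a reader how likely the trial is to detect such an increase.

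**Working it through.** **The plan's own figure.** Two-sided Schoenfeld formula, 1:1 allocation: 4 × (1.960 + 0.842)² / (ln 1.5)² = 190.97, rounded up to 191. The stated number is reproduced exactly, but the formula returns deaths.

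**Inputs from the documents.** Alpha 0.05, HR 1.5, 100 per arm, one-year endpoint, re-allocated share f = 15% (cited range 5% to almost 25%).

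**Assumptions not in the documents.**

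- Control one-year mortality m is 20%, 30%, 40% or 50%.
- One-year mortality p in the re-allocated group, if managed as controls, is 60% to 80%.
- There is no effect where management is unchanged.
- The HR is read as control versus MRI.
- There is no dropout.

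**Formulas.**

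- MRI-arm mortality under HR 1.5: mI = 1 − (1 − m)^(1/1.5).
- Required fall in the re-allocated group: (m − mI)/f.
- MRI-arm mortality if deaths in the re-allocated group are halved: mI = m − 0.5·f·p.
- Overall HR (ratio of one-year cumulative hazards): ln(1 − m)/ln(1 − mI).
- Deaths: D = 100·m + 100·mI.
- Power, beneficial direction only: Φ(ln HR × √D/2 − 1.96).

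**Results at a 15% share.**

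| Control mortality | One-year deaths at HR 1.5 | Power at HR 1.5 | Fall needed in the 15% for HR 1.5 (points) | Overall HR if their deaths are halved | Power of that HR with 191 deaths | Power of that HR on one-year deaths |
|---|---|---|---|---|---|---|
| 20% | 34 | 22% | 41 | 1.32–1.48 | 49–77% | 13–21% |
| 30% | 51 | 31% | 59 | 1.21–1.30 | 26–44% | 11–16% |
| 40% | 69 | 39% | 74 | 1.16–1.23 | 18–30% | 10–14% |
| 50% | 87 | 47% | 87 | 1.14–1.20 | 15–23% | 9–14% |

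The third column is the event-count effect alone. The sixth is dilution alone. The last is both together.

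**The two extreme cells, worked.**

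- m = 0.20, p = 0.80: mI = 0.20 − 0.5 × 0.15 × 0.80 = 0.14. HR = ln 0.80/ln 0.86 = 1.48. D = 20 + 14 = 34. Power = 0.207.
- m = 0.50, p = 0.60: mI = 0.50 − 0.5 × 0.15 × 0.60 = 0.455. HR = ln 0.50/ln 0.545 = 1.14. D = 50 + 45.5 = 95.5. Power = 0.095.

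Log-rank simulations of these two cells (4,000 runs each) gave 0.211 and 0.097.

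**Other shares, deaths halved, on one-year deaths.**

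- At 5%, the overall HR is 1.04 to 1.12 and power about 4% to 5.5%. HR 1.5 cannot be reached, because the required fall exceeds 100 points in every row.
- At 25%, the required falls are 25/35/45/52 points. Power is about 19% to 38% for control mortality of 30% to 50%. At 20% control mortality it reaches 54%, in a degenerate case where every control death lies in the re-allocated group.

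**Upper bound at 15%.** With no deaths at all in the re-allocated group (mI = m − f·p), power on one-year deaths is about 26% to 74%, still below 80%.

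**The case against.** **The 80% is conditional, and the HR is a design choice.** This stands. The sentence names the HR on which the power depends, so the plan does not promise 80% whatever the truth. The complaint is that the 1.5 is neither justified nor reconciled with the flow.

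**The low power could be blamed on dilution alone.** A reader might infer that dilution takes the power from 80% down to 9% to 21%. The figures do not support that. The step from 80% to 22–47% is the event count, before any dilution. In the cell with 20% control mortality and 80% group mortality, the overall HR is 1.48, almost the planned value, and dilution costs one point (22% to 21%). That cell is extreme, since 15 × 0.80 = 12 of the 20 control deaths per 100 fall in the 15% group, but it shows that HR 1.5 cannot be called unattainable at a 15% share.

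**MRI could help by other routes.** The MRI arm may have extra imaging: "If the interval from CT to MRI is >14 days, a new CT will be performed to assure a valid comparator". The budget text before FUTURE PERSPECTIVES refers to "50% of the patients that are expected to have more than 14 days between CT and MRI". MRI also stages the local tumour. The written flow describes no change of management from either. The flow figure is not shown in the text available, so this cannot be fully excluded. If the sponsor relies on such a route, the power paragraph should say so.

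**Existing evidence may support 1.5.** The background reports longer time to recurrence with preoperative MRI, but gives no HR and itself doubts that the finding generalises.

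**Longer follow-up would help.** It adds deaths but leaves the dilution. A mixture-model check over 18 months' accrual and 36 months in total assumed control one-year survival of 60% to 80%, a hazard in the 15% group one to three times that of the rest, and a group HR of 2 to 3. It gave about 71 to 131 deaths and 6% to 15% power.

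**A null result would be misread as no benefit.** A reader might infer that the plan invites this. No passage says so, and the plan commits to publishing inconclusive results.

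**Conclusion.** The point holds as a defect of the power statement. Three parts rest on the documents and arithmetic alone: the 1.5 is underived, about 85% of the MRI arm is managed as controls are, and 191 is a death count.

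The sizes rest on the assumed mortalities, the assumed halving of deaths and the absence of benefit elsewhere. Within those assumptions and at the expected 15% share, power at one year is about 9% to 21%. The split between causes varies. At 20% control mortality the event count accounts for nearly all of the loss (22% falls to 13–21% with dilution). At 50%, dilution is the larger further loss (47% falls to 9–14%).

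The required effect is also demanding. A fall in mortality cannot exceed the mortality itself, so with group mortality of 60% to 80% the 87 points needed at 50% control mortality are out of reach, and the 74 points needed at 40% would mean almost no deaths in the re-allocated patients.

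Confidence in the defect is high. Confidence in any single power figure is no more than medium.

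**What to change.** Restate the power paragraph, keeping 200 patients:

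1. Label 191 as the number of deaths required at HR 1.5.
2. Derive the whole-arm effect from the expected re-allocated share (15%, with 5% and 25% as the range) and from stated, sourced one-year mortality for re-allocated patients and for the others.
3. For each share, give the power on the deaths expected in 200 patients at one year.
4. Show the event-count effect (HR 1.5 on one-year deaths) separately from the dilution effect (the derived HR).
5. State any further route by which MRI is expected to change survival, if the sponsor relies on one.

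For Study III, report the difference in one-year survival with its 95% CI from the Kaplan-Meier estimates, and the hazard ratio as supplementary. The endpoint is one-year survival, and an effect confined to a minority need not give proportional hazards.

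The cost is rewording before analysis. No patients, visits or data are added. The downside is that the stated power becomes much lower and the survival claim weaker.

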MRI may be superior to CT for detection of liver metastases in pancreatic cancer [9]. As liver metastases from resectable pancreatic cancer tend to be small [10], for which MRI (with use of diffusion weighted imaging and liver-specific contrast) has a high sensitivity, routine use of preoperative MRI could be beneficial. However, the feasibility of using MRI in detection of liver metastases in pancreatic cancer patients has been sparsely investigated. One prospective study of 69 pancreatic cancer patients found that almost 25% had liver metastases on MRI that were not visible on CT [11], whereas a retrospective study of 216 patients found that MRI revealed liver metastases in only 5% of patients with CT-assessed non-metastatic pancreatic cancer [12]. The latter study also found a longer time to recurrence after surgery in patients undergoing preoperative MRI, suggesting that preoperative MRI may be beneficial in pancreatic cancer patients. However, they did not provide information on why MRI was performed, and findings are unlikely to be generalizable. Furthermore, only few studies have examined the use of MRI in assessing the local extent of the tumor, suggesting it is not inferior to CT [13, 14].

Thus, MRI may provide a superior alternative to conventional CT in order to improve treatment allocation for pancreatic cancer patients. However, there is a substantial need for high-

quality research to examine this. Specifically, no randomized clinical trial (RCT) has been conducted.

PURPOSE AND OVERALL AIM

[figure not shown]
We propose to conduct a nationwide RCT to examine the feasibility of using MRI for tumor staging and identification of liver metastases in pancreatic cancer patients. *The aim is to improve selection of pancreatic cancer patients for surgery in order to increase overall survival*. Within this RCT, we will conduct three studies outlined below.

STUDY POPULATION AND DESIGN

Patients

200 patients with CT-assessed resectable pancreatic cancer allocated to surgery by the local multidisciplinary tumor board (MDT) will be included. Patients will be randomized to either the intervention (preoperative MRI, n=100) or control/standard-of-care (no preoperative MRI, n=100) arm.

Study design and patient flow

An overview of the proposed study design is shown in Figure 1.

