The MRI will be performed using 1.5 or 3.0 T MR scanners of different vendors. The liver will be scanned using axial and coronal T2W single shot (SS) TSE, axial DWI (minimum b-values of 50 and 800) and axial T1W 3D spoiled gradient echo for gadoxetic acid (Primovist, Bayer Pharma, Berlin, Germany) contrast scans. Both a dynamic contrast scan consisted of; pre-contrast phase, arterial phase (timed using bolus tracking) followed immediately by porto-venous phase; late phase at 2 min and hepato-biliary phase 15 min after contrast injection. The gadoxetic acid contrast will be injected at 1 or 2 mL/s depending of using a dilution 1:1 of gadoxetic acid and saline 9mg/ml or not. The dose will be 0.025 mmol/kg body weight with a maximum of 2.5 mmol using a power injector.

Analysis for metastatic lesions

Each modality will be read anonymized. Both CT and MRI images will be read independently by dedicated radiologist from each participating site as part of the routine work-up in staging pancreatic cancer. The CT scan will be performed as the first examination followed by MRI scan within 14 days after the CT scanning. For all focal hepatic lesions confidence of malignancy will be categorized via a 3-point scale, 1: benign, 2: indeterminate, 3: malignant.

FEASIBILITY

Time schedule

The project will begin in January 2022 and end in December 2024. We will include the patients within the first 18 months of the project period. In the final year of the study period, we will perform data analyses and writing of scientific papers. This will allow for a sufficient follow-up period of all patients (please see *Figure 4* for detailed time schedule).

[figure not shown]

Figure 4. Time schedule.

Scientific and non-scientific personnel

At each institution, one research nurse will be responsible for identification of potential study subjects and, in collaboration with the surgeon, perform the practical work on obtaining informed consent and randomize the patients. The research nurse will also be responsible for each patient's path through the project, *e.g.* schedule the imaging and collect data, and to coordinate the project with the research nurses at the other participating sites.

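### Study II's only stated analysis is an ICC, which on the planned 3-point lesion scores either omits MRI-only lesions or sits near 0, so it does not measure detection

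*Combined protocol and SAP*

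**What the plan says.** All places are in the combined protocol and SAP.

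- **Aim** (Specific study aims, hypotheses and outcomes): "Study II: To assess the ability of MRI to detect liver metastases in pancreatic cancer patients with resectable tumor on CT".
- **Analysis** (Figure 3, Study II column): "Agreement assessed by" an ICC, in the 100 intervention-arm patients. The figure does not give the unit of analysis, the ICC model, the paired variable, or the handling of a lesion seen on one scan only.
- **Scale** (Imaging protocols, Analysis for metastatic lesions): "For all focal hepatic lesions confidence of malignancy will be categorized via a 3-point scale, 1: benign, 2: indeterminate, 3: malignant".
- **Reading** (same section): "Both CT and MRI images will be read independently by dedicated radiologist from each participating site". Under Study design and patient flow, the MRI reader is also "blinded to the patient's identity and initial CT scan". No lesion-matching step is described.
- **Expected MRI findings** (Study design and patient flow): no liver metastases in about 75%; "Non-specific liver lesions on MRI, not seen on CT" in about 10%; liver metastases in about 15%, who are referred to biopsy.
- **Entry** (Patients): "200 patients with CT-assessed resectable pancreatic cancer allocated to surgery by the local multidisciplinary tumor board (MDT) will be included". The background section counts distant metastases as a contraindication to surgery.

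**The concern.** A score exists only where a reader sees a lesion. A lesion visible on MRI alone has an MRI score and nothing to pair it with on CT, and a patient with a clean liver on both scans has no score at all. MRI-only lesions are the findings that Study II is about, and one of the three MRI branches is defined by them. An agreement coefficient needs two scores per unit, so the analyst must either drop the MRI-only lesions or give them a CT value that the plan does not define.

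A second difficulty is that patients enter because CT showed resectable disease. CT findings therefore vary little by design, and an ICC needs variation between subjects. The trial could finish with a Study II coefficient that depends mainly on an unstated convention and does not say how many patients had metastases that MRI found and CT missed.

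**Working it through.** The plan gives no sample size or precision figure for Study II, so there is no figure to reproduce.

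**1. Patients affected.** From the expected shares in 100 patients:

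- Non-specific lesions, stated as not seen on CT: 0.10 x 100 = 10.
- Metastases on MRI: 0.15 x 100 = 15. That CT shows nothing in these patients is inferred from entry as CT-resectable; it is not stated.
- Range: 10 to 10 + 15 = 25. The upper end is a bound.

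**2. Option A: lesions scored on both scans only.** Illustrative assumptions, not in the documents: one lesion per patient; 25 MRI-only lesions (10 scored 2 and 15 scored 3); a further 10, 20, 30 or 40 lesions seen on both scans with identical scores (5, 10, 20 or 30 of them scored 1, the rest scored 2). Share dropped = 25 / (25 + shared). The ICC is the two-way absolute-agreement form.

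| Shared lesions | Share dropped | ICC, pairs only | ICC, unseen = 0 | ICC, unseen = 1 |
|---|---|---|---|---|
| 10 | 25/35 = 71% | 1.00 | -0.12 | -0.04 |
| 20 | 25/45 = 56% | 1.00 | -0.18 | -0.03 |
| 30 | 25/55 = 45% | 1.00 | -0.24 | 0.03 |
| 40 | 25/65 = 38% | 1.00 | -0.27 | 0.06 |

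The 1.00 follows from assuming identical scores on shared lesions. If every shared lesion were scored benign on both scans, there would be no variance and the ICC would be 0/0, undefined. The table shows how much depends on the handling of unseen lesions; it does not forecast the trial's result.

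**3. Option B: all 100 patients, unseen coded as the lowest score.** Assume CT = 0 for everyone and MRI = 0 in 75, 2 in 10 and 3 in 15.

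- MRI mean = (10 x 2 + 15 x 3)/100 = 0.65.
- MRI sum of squares about the mean, S = 10 x 4 + 15 x 9 - 100 x 0.65² = 175 - 42.25 = 132.75.
- With CT constant, each patient's mean is half the MRI score. Between-patient mean square = 2 x (S/4)/99 = 66.375/99 = 0.670.
- The residuals are plus and minus half of (MRI score - 0.65). Residual mean square = 2 x (S/4)/99 = 0.670.
- The numerator of the two-way ICC is the difference of these two mean squares, which is 0. ICC = 0.00 for both the agreement and the consistency form.
- One-way form: within-patient mean square = (175/2)/100 = 0.875, so ICC = (0.670 - 0.875)/(0.670 + 0.875) = -0.13.

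The two mean squares are equal whenever one modality is constant, so the two-way result is 0 whatever MRI finds. Coding the lowest score as 1 also gives 0.00. Metastasis yes/no (MRI 15/100, CT 0/100) gives a two-way ICC of 0.00 and a one-way ICC of -0.08.

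**4. The same data as a proportion.** If 15 of 100 patients have MRI score 3 and CT score 0-2, the estimate is 15%, with an exact (Clopper-Pearson) 95% interval of 8.6% to 23.5%. This speaks directly to the Study II hypothesis, which the ICC in step 3 does not.

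**The case against.** The strongest reply is that nothing in the plan excludes MRI-only lesions. Figure 3 sets Study II in patients, and the patient-flow section already places each MRI-arm patient in one of three categories, one of them defined by absence on CT. The CT side has a patient-level status too, through the entry condition. A per-patient metastasis yes/no comparison would keep everyone, and the proportion with metastases on MRI needs no CT lesion score at all. All of this stands.

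A reader might go further and infer that MRI-only lesions must drop out whichever statistic is used, or that the missing level loses information for good. The documents support neither. Drop-out follows only for a lesion-level analysis restricted to complete pairs. All focal lesions are to be scored on independent reads, so a completed read with no lesion recorded means that none was seen, and a 0 can be derived from it.

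It is also fair that 25 is an upper bound. A metastasis on MRI may have been visible on CT and scored 1 or 2. The budget text expects half of the patients to exceed 14 days between scans, which triggers a new CT that could show some lesions.

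The reply does not rescue the stated analysis. The ICC is the only Study II method named, and applied to the per-patient yes/no variable it is still about 0 when CT is constant. The proportion that would answer the question is not planned.

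**Conclusion.** The point holds as a weakness of the planned analysis. On the 3-point lesion scores, the ICC either leaves out MRI-only lesions (about 10 patients by the plan's own expectation, at most about 25 of 100) or, with unseen coded lowest and CT near-constant by selection, comes out at about 0. Neither version measures detection.

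The count rests on the plan's 75/10/15 split. The zero rests on CT being constant or nearly so; a repeat CT or benign lesions visible on CT would move it somewhat. The 38-71% of lesions dropped in the illustration depends on assumed numbers of shared lesions. The plan should be changed before analysis, and preferably before the reads, so that a blank cannot be confused with a read not recorded.

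**What to change.** - For each patient and each modality, record a score of 0-3: 0 = no focal liver lesion, otherwise the highest score of any lesion. Do this for all 100 intervention-arm patients, and state whether the entry CT or the repeat CT supplies the CT score.
- Show the full 4 x 4 CT-by-MRI table.
- In place of the ICC, make the main Study II result the proportion of patients with MRI score 3 and CT score 0-2, with an exact 95% confidence interval.
- Report alongside it the proportion verified by the biopsy already in the patient flow, so that false-positive MRI calls are not counted as confirmed metastases.
- Keep lesion-level scores as secondary, with a stated rule for matching lesions and for those seen on one scan only.

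Adding a 0 level while keeping the ICC would not be enough, as step 3 of the working shows. The cost is one category and one field on the read form, with no extra scan or reader. The ICC is no longer the main Study II result.
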